**Table 2: Percent Body Surfaces**

Body Area	Percent	Total Percentage
Each Arm	9%	18%
Each Leg	18%	36%
Chest & Abdomen	18%	18%
Back	18%	18%
Head	9%	9%
Pubis	1%	1%

Ref.: Przepiorka et al. Bone Marrow Transplant 1995;15(6):825.

### Stage of Chronic GVHD

**Limited:** Localized skin involvement resembling localized scleroderma with or without liver involvement; no other organ involvement.

**Extensive:** Generalized skin and/or multiple organ involvement.

Ref. Sullivan KM, Blood 1981;57:267.

1 BACKGROUND AND RATIONALE

CA209-812 is a randomized, open-label, Phase 3 Trial of nivolumab plus brentuximab vedotin (nivolumab+BV) versus brentuximab vedotin (BV) in participants who are relapsed/refractory or ineligible for autologous stem cell transplant (ASCT). The central question of the study will be to determine if nivolumab+BV improves progression free survival (PFS) over BV in this patient population. Additional objectives include further characterization of the efficacy [REDACTED] of nivolumab+BV vs. BV in this population.

This statistical analysis plan (SAP) details all analyses that are planned in the Clinical Study Report (CSR) for CA209812 study except for safety which will be documented separately in the Core Safety SAP¹.

Research Hypothesis:

Nivolumab+BV will provide benefit over BV, as evidenced by improvement in PFS assessed by Blinded Independent Central Review (BICR), to participants who are relapsed/refractory or ineligible for autologous stem cell transplant (ASCT).

Schedule of Analyses:

The interim PFS analysis is scheduled when at least 70% (131/187) of final PFS events have been observed with a minimum follow-up of 6 months since the last patient first visit (LPFV), which is projected to occur approximately 40 months after the start of randomization. The final PFS analysis is scheduled when 187 PFS events have been observed, which would occur approximately 45 months after start of randomization (34 months accrual + 11 months follow up). Additional survival follow-up may continue for up to 4 years from the time of the first dose of the last enrolled participant. The study will end once survival follow-up has concluded.

All secondary endpoints will be analyzed at the time of the interim and final PFS analysis.

2 STUDY DESCRIPTION

2.1 Study Design

[figure not shown]
This is a 1:1 randomized, open-label Phase 3 study in advanced cHL participants ≥ 18 years old who are relapsed refractory or ineligible for ASCT. Patients will be balanced in the 2 groups in regards to prior therapies. Approximately 340 participants will be treated in one of 2 arms. In one arm, participants will receive nivolumab 360 mg IV every 3 weeks until progression or unacceptable toxicity (except for patients in CR who can discontinue at 2 years) plus BV 1.8 mg/kg IV every 3 weeks for up to 16 cycles, or until disease progression or unacceptable toxicity, whichever occurs first. In the other arm, participants will receive BV alone 1.8 mg/kg every 3 weeks for up to 16 cycles, disease progression, or unacceptable toxicity, whichever occurs first. Discontinuation of study therapy can also occur if the participant meets other criteria outlined in Protocol Section 8.1. Participants receiving nivolumab who achieve CR may discontinue treatment

after a maximum of 2 years of therapy, provided that there is no prohibitive toxicity. Participants can be brentuximab vedotin-naïve, or can have prior BV treatment as a single agent or in combination in any line of therapy. Randomization stratification will be performed on the following two factors: 1) Prior ASCT status (YES/NO). 2) Prior BV use (YES/NO).

- Duration of study participation: Randomization is within 28 days of the screening. The recruitment period is approximately 34 months with a follow up of 4 years after the last patient first visit (LPFV). Participants will receive active treatment of nivolumab until progression or unacceptable toxicity plus BV for 16 cycles or until progression or unacceptable toxicity, whichever comes first, or BV alone up to 16 cycles, or until progression or unacceptable toxicity, whichever occurs first. Each 21-day dosing period will constitute a cycle. The treatment period will be followed by a survival follow up period.

This study will consist of 3 phases: screening, treatment, and follow-up.

Figure 2.1-1: Study Design

Abbreviations: BV = brentuximab vedotin; BICR = Blinded Independent Central Review; PFS = progression-free survival; CRR = complete response rate; OS = overall survival; ORR = objective response rate; DOCR = duration of complete response; DOR = duration of response; BOR = best overall response

2.2 Treatment Assignment

Participants will be identified and informed consent obtained. Participants must be enrolled into the study by the interactive web response system (IVRS) to obtain the participant number. For both randomized arms, the investigator or designee will register the participant for enrollment by following the procedures established by BMS. The following information is required for registration:

- Date that informed consent was obtained
- Date of birth
- Gender at birth

Once registered, participants who have signed the ICF and met all eligibility criteria will be ready to be randomized. The site will enter into the IVRS to obtain the treatment assignment. Participants will be randomly assigned through IVRS in 1:1 ratio to either arm A (nivolumab+BV) or arm B (BV) stratified by two factors: 1) Prior ASCT status (YES/NO), 2) Prior BV use (YES/NO). The randomization will be carried out via permuted blocks within each stratum. The exact procedures for using the IVRS will be detailed in a separate document.

2.3 Blinding and Unblinding

Not applicable. This is an open-label study.

2.4 Protocol Amendments

None.

2.5 Data Monitoring Committee

An independent Data Monitoring Committee (DMC) will be established to provide oversight of safety and efficacy considerations and to provide advice to the Sponsor regarding actions the committee deems necessary for the continuing protection of participants enrolled in the trial. Details of DMC responsibilities and procedures will be specified in the DMC charter.

3 OBJECTIVES

3.1 Primary Objective

[figure not shown]
- To compare progression free survival of nivolumab+BV vs. BV based on BICR assessments

3.2 Secondary Objectives

Secondary objectives include the following:

- To compare the complete response rate of nivolumab+BV vs. BV based on BICR assessments
- To assess objective response rate and duration of response based on BICR
- To assess duration of complete response based on BICR
- To assess overall survival of participants treated with nivolumab + BV vs BV
- To assess PFS based on investigator assessments

- To assess the overall safety and tolerability of nivolumab in combination with chemotherapy, as measured by incidence and severity of adverse events (AEs), serious adverse events (SAEs), and specific laboratory abnormalities

4 ENDPOINTS

4.1 Primary Endpoints

Progression Free Survival (PFS)

Progression-free Survival (PFS) by BICR: defined as time from date of randomization to the date of death due to any cause or the first documented disease progression as determined by the BICR, whichever occurs first.

Participants who die without a reported progression will be considered to have progressed on the date of their death. Participants who did not progress or die will be censored on the date of their last tumor assessment. Participants who did not have any on study assessments and did not die will be censored on the randomization date. A participant who initiates a subsequent anti-cancer therapy (including allogeneic transplant) will be censored on the date of last tumor assessment prior or on the start date of their subsequent anti-cancer therapy.

The censoring scheme is summarized in Table 4.1-1.

Table 4.1-1: Censoring scheme used in primary analysis of PFS

Situation	Date of Progression or Censoring	Outcome
No baseline tumor assessments	Randomization date	Censored

No on-study tumor assessments and no death	Randomization date	Censored
New subsequent anticancer therapy started without a prior reported progression by BICR or death	Date of last evaluable tumor assessment prior to or on the date of initiation of the subsequent anti-cancer therapy	Censored
Progression per BICR documented at a scheduled or unscheduled visit and no other subsequent anticancer therapy started before	Date of the first documented tumor progression	Progressed
Participant progression free, no death and no subsequent anti-cancer therapy started	Date of last evaluable tumor assessment	Censored
Death without prior progression per BICR and no subsequent anticancer therapy started	Date of death	Progressed

4.2 Secondary Endpoints

4.2.1 BOR, CRR, ORR, PR, TTR, DOR and DOCR

Best Overall Response (BOR) of CR or PR or SD or PD will be evaluated for response evaluable participants according to the 2014 Lugano classification, based on BICR assessment.

The BOR is defined as the best response designation recorded between the date of randomization and the date of initial objectively documented progression per the 2014 Lugano classification or the date of subsequent therapy, whichever occurs first. For participants without documented progression or subsequent therapy, all available response designations will contribute to the BOR determination. For participants who continue treatment beyond progression, the BOR should be determined based on response designations recorded up to the time of the initial BICR defined progression.

Complete Response Rate (CRR): defined as proportion of participants who have achieved complete response (Lugano 2014 conference) as determined by the BICR prior to initiating any subsequent therapy among the randomized participants. For participants who continue treatment beyond progression, the complete response should be determined based on response designations recorded up to the time of the initial BICR defined progression.

ORR is defined as the number of participants with a Best Overall Response (BOR) of CR or PR, per the 2014 Lugano classification, based on BICR assessment, divided by the number of randomized participants

The objective response will be further characterized by the time to response (TTR). TTR is defined as the time from first dosing date to the date of the first response, based on BICR assessment. . TTR will be evaluated for responders only.

DOR is defined as the time from first response (CR or PR) to the date of initial objectively documented progression as determined using the 2014 Lugano classification or death due to any cause, whichever occurs first. For participants who neither progress nor die nor received

subsequent anti-cancer therapy, the DOR will be censored on the date of their last tumor assessment. Participants who start subsequent anti-cancer therapy without a prior reported progression will be censored at the last tumor assessment prior to or on the date of initiation of the subsequent anticancer therapy. The censoring scheme of DOR will be the same as the primary censoring scheme for PFS. This endpoint will only be evaluated in participants with objective response of CR or PR.

DOCR is defined as the time from first complete response (CR) to the date of initial objectively documented progression as determined using the 2014 Lugano classification or death due to any cause, whichever occurs first. The censoring scheme of DOCR will be the same as the primary censoring scheme for PFS. This endpoint will only be evaluated in participants with objective response of CR.

[figure not shown]
The other secondary efficacy endpoints include BOR, BOR, CRR, PR, TTR, DOR, and DOCR assessed by investigator.

[figure not shown]
4.2.2 Overall Survival

[figure not shown]
Overall Survival (OS): defined as the time between the date of randomization and the date of death. Participants who are alive at the time of analysis will be censored by last unknown alive date (LKAD).

4.2.3 Safety and Tolerability

Safety will be analyzed through the incidence of deaths, adverse events, serious adverse events, adverse events leading to discontinuation, adverse events leading to dose delay, select adverse events and specific laboratory abnormalities (worst grade) in each treatment group. Toxicities will be graded using the National Cancer Institute (NCI) Common Terminology Criteria for Adverse Events (CTCAE) version 4.0. See details in the Core Safety SAP.

5 SAMPLE SIZE AND POWER

The planned sample size for this study will be approximately 340 randomized participants. The sample size of the study accounts for the primary efficacy endpoint, PFS. PFS will be evaluated for treatment effect at the overall alpha level of 0.05 (two-sided) with 90% power.

[figure not shown]

Table 5.1 summarizes the expected timing of each analysis. East version 6.3 was used for sample size/power computations.

Table 5.1 Schedule of Analyses

	Interim Analysis	Final Analysis
Conditions	At least 131 PFS events and 6 months follow-up	At least 187 events
Expected timing	40 months (34 months + 6 months of follow-up)	45 months (34 months+ 11 months of follow-up)
Alpha level	Interim PFS analysis projected at 0.0148 level ^a	Final PFS analysis projected at 0.0455 level

a. Using O'Brien and Fleming alpha spending function in case exact 131 PFS events are observed at the interim PFS analysis

6 STUDY PERIODS, TREATMENT REGIMENS AND POPULATIONS FOR ANALYSES

6.1 Study Periods

See Core Safety SAP.

[figure not shown]
6.2 Treatment Regimens

The treatment group “**as randomized**” will be retrieved from the IVRS system

- Arm A: Experimental Arm nivolumab+BV.
- Arm B: Control arm BV.

The treatment group “**as treated**” will be the same as the arm randomized by IVRS. However, if a participant received the incorrect drug for **the entire period** of treatment, the participant’s treatment group will be defined as the incorrect drug the participant actually received.

6.3 Populations for Analyses

- **All enrolled participants:** All participants who signed an informed consent form and were registered into the IVRS. Analyses of the patients enrolled into the study but not randomized and the reason for not being randomized will be performed on the data set of all enrolled participants.
 - **All randomized participants:** All participants who were randomized to any treatment group in the study. This is the primary dataset for analyses of demography, protocol deviations, baseline characteristics, efficacy, [REDACTED].
 - **All treated participants:** All participants who received at least one dose of study medication. This is the primary dataset for dosing and safety.
 - **Response evaluable participants:** randomized participants whose change in the sum of diameters of target lesions was assessed (i.e.: target lesion measurements were made at baseline and at least one on-study tumor assessment).
- 

7 STATISTICAL ANALYSES

7.1 General Methods

Unless otherwise noted, the bulleted titles in the following subsections describe tabulations of discrete variables, by the frequency and proportion of participants falling into each category, grouped by treatment (with total). Percentages given in these tables will be rounded and, therefore, may not always sum to 100%. Continuous variables will be summarized by treatment group (with total) using the mean, standard deviation, median, minimum and maximum values.

Time to event distribution (e.g. progression free survival, overall survival and duration of response) will be estimated using Kaplan Meier techniques.

Median survival time along with 95% CI will be constructed based on a log-log transformed CI for the survivor function $S(t)$ ^{5,6}. Rates at fixed timepoints (e.g. PFS at 6 months) will be derived from the Kaplan Meier estimate and corresponding confidence interval will be derived based on Greenwood formula for variance derivation and on log-log transformation applied on the survivor function $S(t)$ ⁷.

Unless otherwise specified, a stratified log-rank test will be performed to test the comparison between time to event distributions (e.g. PFS and OS). Stratification factors will be prior ASCT status (YES/NO) and prior BV use (YES/NO).

Unless otherwise specified, the stratified hazard ratio between 2 treatment groups along with CI will be obtained by fitting a stratified Cox model with the treatment group variable as unique covariate.

The difference in rates between the two treatment groups along with their two-sided 95% CI will be estimated using the following Cochran-Mantel-Haenszel (CMH) method of weighting⁸, adjusting for the stratification factors:

$$\hat{\theta} = \frac{\sum_i w_i \hat{\theta}_i}{\sum_i w_i} \sim N \left[\theta, \frac{\sum_i w_i^2 \left[\frac{p_{ix}(1-p_{ix})}{n_{ix}-1} + \frac{p_{iy}(1-p_{iy})}{n_{iy}-1} \right]}{\left(\sum_i w_i \right)^2} \right]$$

where $\hat{\theta} = p_{ix} - p_{iy}$ is the rate difference of the i th stratum, $w_i = \frac{n_{ix}n_{iy}}{n_{ix} + n_{iy}}$, and n_{ix} and n_{iy} are the number of participants randomized to treatments x and y, respectively, in the i th stratum.

Stratification factors will be same as above. Associated odds-ratio will be derived.

P-values from sensitivity analyses are for descriptive purpose only and there will be no multiplicity adjustment for these analyses.

7.2 Study Conduct

7.2.1 Accrual

The accrual pattern will be summarized per country, investigational site and per month for all enrolled participants. Randomization date, first dosing date, country, investigational site will be presented in a by participant listing of accrual.

7.2.2 Relevant Protocol Deviations

The relevant Protocol Deviations will be only summarized for all randomized participants, by treatment group and overall. The following programmable deviations from inclusion and exclusion criteria will be considered as relevant protocol deviations. Non-programmable relevant eligibility and on-treatment protocol deviations, as well as significant (both programmable and non-programmable) eligibility and on-treatment protocol deviations will be reported through ClinSIGHT listings.

At entrance:

- Participants without either measurable disease at baseline or FDG avid by PET
- Participant with baseline ECOG >1

On-Study:

- Participants receiving concurrent anti-cancer therapy other than nivolumab or BV.
- Participant treated differently as randomized (participants who received the wrong treatment, excluding the never treated).

A summary table and a by participant listing of relevant protocol will be produced.

7.3 Study Population

7.3.1 Subject Disposition

The total number of participants enrolled (randomized or not randomized) will be presented along with the reason of not being randomized. This analysis will be performed only on the all enrolled population only.

Number of participants randomized but not treated along with the reason will be tabulated by treatment group as randomized. This analysis will be performed only on the all randomized population only.

Number of participants who discontinued treatment along with corresponding reason will be tabulated by treatment group as treated. Reason for discontinuation will be derived from participant status CRF page. This analysis will be performed only on the all treated participants population.

A participant listing for all randomized participants will be provided showing the participant's randomization date, first and last dosing date, off study date and reason for going off-study. A participant listing for participants not randomized will also be provided, showing the participant's race, gender, age, consent date and reason for not being randomized.

7.3.2 Demographics and Other Baseline Characteristics

Descriptive statistics will be summarized the following baseline characteristics for all randomized participants by treatment group as randomized. All baseline presentations will identify participants with missing measurements.

- Age (descriptive statistics)
- Age categories (<30 , ≥ 30 and <45 , ≥ 45 and <60 , ≥ 60)
- Gender (male, female)
- Race (white, black, asian, other)
- Baseline ECOG Performance Status (0, 1)
- Weight (descriptive statistics)
- Time from initial disease diagnosis to first dose of study medication (< 3 months ; ≥ 3 months)
- Prior ASCT status (YES/NO)
- Prior BV use (YES/NO).
- Region (US/Canada, Europe, Rest of the World)
- Smoking Status (Yes, No, Unknown)
- Disease stage at initial diagnosis (stage 1 or 2, 3, 4)
- International Prognostic Score (IPS) (0-2, 3 or higher) at initial diagnosis
- Disease stage at study entry (stage 1 or 2, 3, 4)
- B-symptoms at baseline (absent, present)
- Specific B-symptoms at baseline (Fever, Night Sweats, Weight Loss)
- Bulky disease at baseline (Yes, No, Not Available)
- Extra lymphatic involvement at baseline (Yes, No, Not Available)
- Lymphoma involvement in bone marrow at baseline (Yes, No, Not Available)
- All lesions (Investigator Tumor Assessments at Baseline): sites of diseases, number of disease sites per participant
- Target Lesions (Investigator Tumor Assessments at Baseline): Presence of target lesions, site of target lesion, sum of product diameters of target lesions.

7.3.3 Medical history- Concurrent diseases

General medical history will be listed by participant and pretreatment events will be tabulated.

7.3.4 Prior therapy agents

The following will be summarized:

- Number of participants by type of prior therapy received (excluding preparative regimen for ASCT): immunomodulatory derivatives (e.g. lenalidomide), other chemotherapy, immunotherapy by monoclonal antibodies (e.g. Rituximab, Brentuximab)

- Number of participants by type of regimen for first and second lines of therapy (e.g. ABVD, ICE, BEACOPP, Stanford V)
- Number of participants by type of regimen received for preparation to ASCT (BEAM, CBV, Other)
- Number of prior systemic regimens received (1, 2, 3, 4, ≥ 5), excluding preparative regimen before and after ASCT
- Best response to regimen before most recent ASCT
- Disease Status at most recent ASCT
- Best response to most recent ASCT
- Time from completion of most recent prior regimen to treatment (< 3, 3 - 6, > 6 months)
- Prior radiotherapy (yes or no)

Other Prior therapy:

- Prior/current non-study medication classified by anatomic and therapeutic classes.

Medication will be reported using the generic name. A listing by participant will also be provided.

7.3.5 Baseline examinations

Participants with abnormal baseline physical examination will be tabulated by examination criteria and by treatment group.

7.4 Extent of Exposure

Analyses in this section will be performed in all treated participants by three treatment groups as treated.

7.4.1 Administration of study therapy

The following parameters will be summarized (descriptive statistics) by drug (nivolumab or BV) and treatment group:

- Relative dose intensity (%) using the following categories: < 50%; 50 - < 70%; 70 - < 90%; 90 - < 110%; $\geq 110\%$.
- Number of doses received for each drug (summary statistics).
- Cumulative dose
- Number of cycles received.

Duration of treatment will be presented by treatment group using a Kaplan-Meier curve whereby the last dose date will be the event date for those participants who are off study therapy. Median duration of treatment and associated 95% CI will be provided. Participants who are still on study therapy will be censored on their last dose date.

A by-participant listing of dosing of study medication (record of study medication, infusion details, and dose change) and a listing of batch number will be also provided.

Below table summarizes the key parameters used to calculate dosing data.

Table 7.4.1-1: Administration of study therapy: definition of parameters

	Nivolumab	BV
Dosing schedule per protocol	360mg every 3 weeks	1.8 mg/kg every 3 weeks
Dose	Dose (mg) is defined as Total Dose administered (mg). Dose administered in mg at each dosing date on the CRF.	Dose (mg/kg) is defined as Total Dose administered (mg) / most recent weight (kg). Dose administered in mg at each dosing date and weight are collected on the CRF.
Cumulative Dose	Cum dose (mg) is sum of the doses (mg) administered to a participant during the treatment period.	Cum dose (mg/kg) is sum of the doses (mg/kg) administered to a participant during the treatment period.
Relative dose intensity (%)	$\text{Cum dose (mg)} / [(\text{Last dose date} - \text{Start dose date} + 21) \times 360 / 21] \times 100$	A: $\text{Cum dose (mg/kg)} / [(\text{Last dose date} - \text{Start dose date} + 21) \times 1.8 / 21] \times 100$
Duration of treatment	Last dose date - Start dose date +1	Last dose date - Start dose date +1

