### **Nivolumab and Brentuximab vedotin arm**

Participants should receive nivolumab at a dose of 360 mg as a 30-minute infusion on Day 1 of each treatment cycle until progression, unacceptable toxicity, withdrawal of consent, or the study ends, whichever occurs first. No dose escalations or reductions of nivolumab are allowed. Premedications are not recommended for the first dose of nivolumab. For 30-minute infusions, infusion durations are  $\pm 5$  minutes. For Q3W dosing cycles, participants may be dosed within a  $\pm 3$  day window.

For participants in the nivolumab/BV arm, BV will be administered first as a 30-minute infusion followed by a minimum 30-minute rest prior to the nivolumab infusion. Brentuximab vedotin will be administered as a 1.8 mg/kg dose on Day 1 of each treatment cycle every 3 weeks for 16 cycles. In the absence of infusion-related reactions, the infusion rate for all participants should be calculated in order to achieve a 30-minute infusion period. Brentuximab vedotin must not be administered as an IV push or bolus nor mixed with other medications. Dosing of BV is based on participant's actual body weight. Doses must be adjusted for participants who experience a  $\geq 10\%$  change in weight from baseline. Other dose adjustments for changes in body weight are permitted per institutional standard. An exception to weight-based dosing is made for participants weighing greater than 100 kg; doses will be based on 100 kg for these individuals. Rounding is permissible within 5% of the nominal dose.

Nivolumab Injection, 100 mg/10 mL (10 mg/mL) is to be administered as an IV infusion through a 0.2-micron to 1.2-micron pore size, low-protein binding in-line filter at the protocol-specified doses. It is not to be administered as an IV push or bolus injection. Nivolumab injection can be infused undiluted (10 mg/mL) or diluted with 0.9% Sodium Chloride Injection, USP or 5% Dextrose Injection, USP to protein concentrations as low as 1 mg/mL. Instructions for dilution and infusion of nivolumab injection may be provided in the clinical protocol, pharmacy binder, or pharmacy reference sheet. Care must be taken to assure sterility of the prepared solution as the product does not contain any antimicrobial preservative or bacteriostatic agent.

Nivolumab infusions are compatible with polyvinyl chloride (PVC) or polyolefin containers and infusion sets, and glass bottles.

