### **Brentuximab Vedotin arm**

Brentuximab Vedotin will be administered as a 1.8 mg/kg dose on Day 1 of each treatment cycle every 3 weeks for 16 cycles as a 30-minute infusion. In the absence of infusion-related reactions, the infusion rate for all participants should be calculated in order to achieve a 30-minute infusion period. Brentuximab vedotin must not be administered as an IV push or bolus nor mixed with other medications. Dosing of BV is based on participant's actual body weight. Doses must be adjusted for participants who experience a  $\geq 10\%$  change in weight from baseline. Other dose adjustments for changes in body weight are permitted per institutional standard. An exception to weight-based dosing is made for participants weighing greater than 100 kg; doses will be based on 100 kg for these individuals. Rounding is permissible within 5% of the nominal dose.

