## **9.3 Overdose**

An overdose is defined as the accidental or intentional administration of any dose of a product that is considered both excessive and medically important. All occurrences of overdose must be reported as an SAE (see Section 9.2).

For this study, any dose of nivolumab greater than 10 mg/kg within a 24-hour time period will be considered an overdose. Also, any dose of BV exceeding 180 mg in a 24-hr period will be considered an overdose.

In the event of an overdose the [investigator/treating physician] should:

- 1) Contact the Medical Monitor immediately
- 2) Document the quantity of the excess dose as well as the duration of the overdosing in the CRF

Decisions regarding dose interruptions or modifications will be made by the investigator in consultation with the Medical Monitor based on the clinical evaluation of the participant.

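### The SAP's relative dose intensity for BV ignores the protocol's 100 kg dosing cap, so full on-schedule dosing scores below 100% in anyone heavier

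*SAP*

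**What the plan says.** **Protocol Section 7.1**, with the same rule in both arms. The planned dose is: "Brentuximab Vedotin will be administered as a 1.8 mg/kg dose on Day 1 of each treatment cycle every 3 weeks for 16 cycles". The weight basis is: "Dosing of BV is based on participant's actual body weight". There is one exception: "An exception to weight-based dosing is made for participants weighing greater than 100 kg", for whom "doses will be based on 100 kg for these individuals". Rounding within 5% of the nominal dose is allowed. Section 9.3 adds that "any dose of BV exceeding 180 mg in a 24-hr period will be considered an overdose".

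**SAP Section 7.4.1, Table 7.4.1-1.** The BV dose in mg/kg is "Total Dose administered (mg) / most recent weight (kg"). The cumulative dose "is sum of the doses (mg/kg) administered to a participant during the treatment period". Relative dose intensity (RDI) is that cumulative dose divided by (last dose date - start dose date + 21) x 1.8/21, times 100. It is reported in the bands "< 50%; 50 - < 70%; 70 - < 90%; 90 - < 110"%, plus a top band from 110%.

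**SAP Section 7.4.2.3** uses the same calculated dose to assign a BV dose level: Level 0 at 1.35 mg/kg or more, Level -1 below that. After Cycle 1, a reduction is recorded when the level is lower than at the previous dose.

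No SAP text mentions the 100 kg cap or adjusts for it.

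**The concern.** RDI is meant to show how much of the planned drug was given. The table's own first row sets out the schedule per protocol as the yardstick. For nivolumab, and for BV at 100 kg or below on a dose matched to current weight, full dosing on schedule scores 100%. Above 100 kg the two sides of the BV ratio use different rules: the dose given is fixed by the cap, while the divisor and the 1.8 mg/kg target are not.

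To score 100% under the SAP formula, a 120 kg participant would need 1.8 x 120 = 216 mg per dose. That exceeds the 180 mg above which Protocol 9.3 speaks of an overdose.

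What is at stake is the accuracy of the exposure tables, which give the context for the descriptive safety results. The dose-reduction counts inherit the same problem.

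**Working it through.** The plan states no RDI value, so there is no figure to reproduce. The check applies the SAP formula to a participant who gets every protocol dose on schedule.

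**Inputs**
- Dose given, Protocol 7.1: 1.8 x min(W, 100) mg, where W is weight in kg. Above 100 kg this is 1.8 x 100 = 180 mg, which equals the threshold in Protocol 9.3.
- SAP dose, Table 7.4.1-1: mg given / W.
- Weights: an assumption. The documents give no weight distribution and no upper weight limit. The range shown is 100 to 150 kg.

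**RDI.** For n doses given 21 days apart, last minus start date plus 21 is (n - 1) x 21 + 21 = 21n days. Then

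RDI = n x [1.8 x min(W, 100)/W] / [21n x 1.8/21] x 100 = 100 x min(W, 100)/W.

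The number of cycles cancels. Above 100 kg this is 100 x 100/W percent.

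| Weight (kg) | SAP dose (mg/kg) | SAP RDI | SAP band | SAP dose level | RDI with capped divisor |
|---|---|---|---|---|---|
| 100 | 1.800 | 100.0% | 90 - < 110% | 0 | 100.0% |
| 105 | 1.714 | 95.2% | 90 - < 110% | 0 | 100.0% |
| 110 | 1.636 | 90.9% | 90 - < 110% | 0 | 100.0% |
| 112 | 1.607 | 89.3% | 70 - < 90% | 0 | 100.0% |
| 120 | 1.500 | 83.3% | 70 - < 90% | 0 | 100.0% |
| 130 | 1.385 | 76.9% | 70 - < 90% | 0 | 100.0% |
| 140 | 1.286 | 71.4% | 70 - < 90% | -1 | 100.0% |
| 150 | 1.200 | 66.7% | 50 - < 70% | -1 | 100.0% |

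**Where the band changes**
- Below 90%: W > 180/(1.8 x 0.90) = 111.1 kg.
- Below 70%: W > 180/(1.8 x 0.70) = 142.9 kg.
- With doses at 0.95 to 1.05 of nominal, the first point ranges from 105.6 to 116.7 kg and the second from 135.7 to 150.0 kg. The upper ends need a dose of 189 mg, above the 180 mg threshold in Protocol 9.3.

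**Dose level.** An unchanged 180 mg dose falls below the SAP cut when W > 180/1.35 = 133.3 kg. Two errors follow:
- *False reduction.* A participant whose weight rises from 133 to 134 kg on 180 mg goes from 1.353 to 1.343 mg/kg, so from Level 0 to Level -1, with no change in dose.
- *Missed reduction.* A 135 kg participant on 180 mg is at 180/135 = 1.33 mg/kg. Taking the 1.2 mg/kg reduced dose in Protocol Table 7.4.2-1 on the 100 kg basis gives 120 mg, or 120/135 = 0.89 mg/kg. Both are Level -1, so the reduction is not counted. With the capped divisor the doses are 1.8 and 1.2 mg/kg, and it is counted.

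**The case against.** The case against concerns reach rather than arithmetic, and much of it stands.

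- **Nobody may be affected.** The SAP lists weight only as a baseline summary, and nothing shows that any of the 23 randomized participants exceeds 100 kg. This stands.
- **The category table is more robust than the RDI value.** Apart from rounding, a fully dosed participant between 100 and 111 kg stays in the 90 - < 110% band. A reader might infer that every heavier participant is reported as under-dosed. The documents do not support that: the band does not change until about 111 kg, and the SAP nowhere treats a low RDI as under-dosing or lists it among the relevant protocol deviations.
- **The arms are treated alike.** A reader might also infer that the comparison between arms is distorted. The cap and the formula apply to BV identically in both arms, no test is attached to exposure, and Protocol Section 10 now rules out formal testing. Any difference would need an imbalance in heavy participants, on which the documents are silent. The by-participant dosing listing would also show the doses given.
- **Cumulative mg/kg is not an error.** A 150 kg participant given 180 mg did receive 1.2 mg/kg. Capping that divisor would report 1.8 mg/kg and misstate exposure per kg. This stands and limits the fix.
- **Steady weight above 133.3 kg does not create a false reduction.** The participant is Level -1 throughout. This is correct, but it is also why a true reduction in that person is missed.
- **The cap does not make RDI exact for everyone.** The protocol requires dose adjustment only at a weight change of 10% or more. Someone going from 70 to 76 kg on an unchanged dose scores 70/76 = 92.1%, or 87.5% with 5% downward rounding. This is a separate limitation that the fix does not address.

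None of this answers the central point: above 100 kg the SAP measures BV against a dose that the protocol does not plan.

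**Conclusion.** The RDI rule is wrong as written for any participant above 100 kg, and the dose-level rule can misclassify around and above 133.3 kg. The understatement at full dosing is 1 - 100/weight: 4.8 percentage points at 105 kg, 16.7 at 120 kg and 33.3 at 150 kg.

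The practical effect is small and possibly nil, because it depends on weights that the documents do not give. If the 23 participants split 11 and 12 and all were treated (an assumption), one misclassified person would move a band by 1/12 to 1/11, or 8.3 to 9.1 percentage points. Efficacy results do not use these quantities. The point takes no view on the BV dose or the cap itself. It asks only that planned exposure be measured by the protocol's own rule.

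**What to change.** In SAP Table 7.4.1-1, add a BV dose variable for RDI: total dose administered (mg) / min(most recent weight, 100 kg). Use its sum as the RDI numerator, with the denominator unchanged. Capping the planned dose in the denominator at 1.8 x 100 = 180 mg would also restore 100% for full dosing.

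Use the same capped dose for the dose-level classification in SAP 7.4.2.3.

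Keep the cumulative dose in mg/kg on actual weight, with a footnote saying so. Because the RDI formula now draws on that row, the two quantities must be named separately.

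The cost is one formula in the SAP and its program. Protocol Section 10.3 has the SAP finalized before database lock, and SAP Section 9 puts all its analyses in the final report, so that is the natural point to make the change.
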